1.0 Objectives / Specific Aims

Feeding difficulty is the primary reason for prolonged hospitalization for preterm and term infants in the US, and often requires significant interventions including gastrostomy tube (Gtube) placement to attain adequate nutrition for discharge home. Preterm infants who have CNS dysmaturation or other brain injury and term infants who have had hypoxic ischemic brain injury (HIE) commonly have oromotor dyscoordination, resulting in feeding difficulty. Suck-swallow-breathe is a complex sensory-motor sequence that infants with brain injury must learn and master to take all feeds by mouth (po) and be discharged home. Current standard of care involves daily oral stimulation or feeding practice with therapists, nurses or parents. The scope of the problem is significant. A recent study by the Neonatal Research Network of 6017 moderately preterm infants shows that 37% remain hospitalized beyond 36 weeks due to feeding difficulty. Correspondingly, G-tube placement has doubled from 2002 to 2012. Among preterm infants born between 23-33 weeks gestation, 5.5% of had G- tubes placed for feeding difficulties. Novel therapies are needed to improve oromotor learning and decrease hospital length of stay for these infants at high risk of developmental delay.

Transcutaneous auricular vagus nerve stimulation (taVNS) is a non-invasive form of vagus nerve stimulation, which facilitates activity-dependent neuroplasticity and improves functional motor outcomes when paired with behavioral interventions in adults post stroke.^{5, 6} In a first-in-infants pilot study we paired stimulation (taVNS) with bottle feeding to enhance motor learning of feeding in preterm or term HIE infants, who were failing oral feeds.⁷ Out of 30 infants to date whose clinical treatment plan was to have immediate placement of a G-tube, 52% were able to achieve full oral feeds with taVNS.⁸ We observed no adverse effects of pain or bradycardia. Additionally, infants treated twice daily required less time to full po feeds than infants treated oncedaily, without safety risk. Heart rate (HR) decreased transiently at stimulation onset, which served as a reliable marker of vagus target engagement. taVNS-paired feeding was well accepted by parents and care providers.

During this pilot trial, our team developed a custom closed-loop taVNS-paired feeding system: a bulky analog system consisting of an EMG system paired with a computerized electrical stimulation system, mountedon a cart, and connected to wired electrodes. For further clinical trial testing and commercialization, we need aless expensive compact set-up that is easy to use. The company, FRD Accel, will collaborate with Soterix, a manufacturer of electronic pulse generators (EPG) to develop this product with the taVNS pioneers at Medical University of South Carolina and test it in infants: [name], a clinical neonatologist and translational scientist, [name], an expert in the technical development of taVNS, and [name], a mentor in early taVNS development with a record of moving multiple neuromodulation-based therapies through FDA approval and market acceptance. FRD Accel will develop and gather clinical data on a portable, switch-triggered taVNS system in this phase I proposal to include in our FDA application.

Aim 1. Develop the BabyStrong taVNS-paired bottle system. The device will feature an on/off switch on a sleeve designed to slip onto any bottle, a wired connection to a small, programmable EPG to deliver pulsedelectrical stimulation in 0.1mA increments, and wired ear electrodes. In aim 1 we will:

- 1) Bench test the device for accuracy of microcurrent delivery in small (0.1mA) increments;
- 2) Verify target engagement with reproducible HR decrease with active stimulation in adult volunteers:
- 3) **Refine the system** with feedback from parent advisor and nurses on the ease of

operability of theswitch-on-sleeve design, and the EPG and ear electrodes.

Criteria for success for Aim 1: Confirmation of reliable waveform (0.1mA increments) using benchtop oscilloscope, & passing electrical stress tests on all components; HR decrease of 5-10bpm with onset of active stimulation in adult volunteers, indicating target engagement; Approval of design by parent advisor and nurses.

Aim 2. Conduct a small-scale safety and efficacy study of the BabyStrong portable taVNS feeding system. We will test the prototype BabyStrong feeding system using active (n=10) and sham (n=10) taVNS ininfants with twice daily A or B treatment for 10 days, with cross over to B/A treatment if there is no progress with feeds. The treatment assignment will be blinded to care providers and parents. We will compare daily po volumes over 10 days prior and the 10 days of treatment. Safety measures will be bradycardia and discomfort.

Criteria for success of BabyStrong feeding system: No sustained increase in discomfort scores or bradycardia; attainment of full oral feeds in 50% ofinfants.

Success of Phase I aims will position us well for Phase II and a pivotal RCT clinical trial with cross-over design, to determine if the BabyStrong system allows preterm and term infants with feeding failure to be discharged sooner and avoid costly complications as well as prolonged hospital stays. If successful, the BabyStrong device could have significant impact on the infants, their families, and hospital costs, as well as set the stage for greater use of taVNS targeted plasticity in neurodevelopmental disorders like cerebral palsy.

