Non-Significant Risk device designation: We have IRB approval for two pilot studies in preterm and term infants using the custom modified devices and taVNS study procedures proposed in this application. The taVNS systems have non-significant risk device designations from MUSC's IRB in our pilot trials.

Proposed Trial of BabyStrong taVNS feeding system

We will conduct a small-scale safety and efficacy study of several versions of the prototype BabyStrong portable taVNS feeding system. We will test the prototypes using a maximum of active (n=10) or sham (n=10) taVNS in infants with twice daily A/B treatment for 10days, with crossover to B/A treatment if there is no progress with feeds. Care providers, study personnel and parents will be blinded to treatment assignment.

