4.0 Study Endpoints

Primary outcome: We will compare the numbers of infants who attain full oral feeds (> or = 130ml/kg/d with weight gain). We do not anticipate having power to compare any outcome with valid statistical measures.

Primary Safety Outcomes: Bradycardia (HR<80bpm for 5 seconds); discomfort measured by Neonatal andInfant Pain scale (NIPS) >3 point change, equivalent to pain with heelstick for blood drawing ^{34, 35}.

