5.0 Inclusion and Exclusion Criteria/ Study Population

Inclusion criteria: Infants born at any GA, failing oral feeds after trying to learn feeding for 2 weeks if term, and 4 weeks if preterm, who are deemed safe to po every feed without volume limitations by OT/SLP, and who the clinical team has determined will likely need a G-tube.

Exclusion criteria: Cardiomyopathy, unstable bradycardia, significant respiratory support, or infants of poorly controlled diabetic mothers, defined by obstetrical care providers and HgbA1C>5.6% or ketonuria.

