8.0 Recruitment Methods

The clinical team will refer parents for participation if their infants are failing oral feeds and are approaching G-tube placement per unit guidelines. [name] will also screen EPIC (chart review) for infants in the nursery with known brain injury that may have poor feeding, such as perinatal arterial stroke, HIE, severe IVH, PVL or cerebellar infarct, regardless of sex or race.

After screening and consent we will randomize infants to receive either active or sham taVNS. The assignment will be blinded to care providers, investigators and parents. Recruitment of 20 infants in 9 months will require enrolling 2-3 infants/mo. In the pilot study we frequently were unable to accommodate all requests, due to equipment limitations. With several BabyStrong units, we anticipate no problems completing enrollment.

Infants of all ethnicities and racial categories will be accepted into this study protocol. No preference will be given based on race, gender or ethnicity. Young infants who had perinatal complications leading to perinatally acquired brain injury are **vulnerable** populations and are the target of this proposal.

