10.0 Study Design / Methods

Phase I Protocol:

MRI scan: We will obtain an unsedated diffusion scan on our clinical Siemens 3T MRI prior to initiating treatment and at the end of the 10day treatment period for all infants (2 scans if no cross over) and again at the end of the 7d alternative treatment if applicable (3 total scans for those infants who receive cross-over treatment).

Active taVNS treatment: The study team will determine the PT daily, then the nurse, therapist or parent will deliver active taVNS at 0.1mA less than the PT, with one of the BabyStrong prototypes during 2 bottle feeds a day. We will record the HR, NIPS scores by nurses before, during taVNS, and whether current is decreased for NIPS.

Sham treatment will use one of the BabyStrong prototypes via on/off switch as for active taVNS. We will test the PT with active stimulation, as care providers expect a brief HR decrease. We will then program a sham setting on the TENS unit to deliver no current after the PT is determined. We will check integrity of sham protocol by de-identified survey of nurses and parents, asking which treatment condition they thought the infant had received.

Cross—over treatment: If progress in daily oral feeding volumes is <4ml/kg/d (based on response rate in pilot trial) after 10 days with either treatment A or B, we will offer cross-over to the alternate treatment. If no further progress is noted after 7 days on alternate treatment, parents and the clinical team will arrange for a G- tube. Any parent can decide to withdraw the baby from the study at any time.

Breast feeding will be allowed, and we can stimulate with breast feeding, if the parent desires. We will offer bottle supplementation ad lib post-BF, and count this as a full volume feed, per standard clinical practice.

Training for safety using a variety of feeders: All individuals, including pediatric speech and languagepathologist (SLP), OT, nurses and parents who feed infants using this device will undergo training on the device operation by study staff. Research staff will supervise all feeders during the taVNS feedings. All feeds will be done in the NICU

The alternative treatment is the usual and customary occupational or speech therapy services which the infant has already been receiving, or to get a G-tube.

Safety measures:

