12.0 Data Management

Power Analysis: We do not anticipate being powered to determine efficacy in feeding response rate, or test for A/B or B/A effects

Keeping Data Confidential: We will assign study numbers to each participant, keep CRF and consent forms in locked offices. Database files with names and contact information will be password protected and stored on the MUSC Pediatric server. All other data files related to this study will be identified by participant number only, without link to standard identifiers. We will publish the aggregate data only.

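### The only stated comparison of daily oral volumes is before versus during treatment, which mixes any device effect with maturation and regression to the mean although a randomised sham arm is available

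*Protocol*

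**What the plan says.** Section 1.0, Aim 2, describes the infant study as "using active (n=10) and sham (n=10) taVNS", given for 10 days with possible crossover, and then states the volume comparison: "We will compare daily po volumes over 10 days prior and the 10 days of treatment". The sentence names two periods and no arms.

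The control arm is sound. Section 8.0 says "After screening and consent we will randomize infants to receive either active or sham taVNS", and section 3.0 says "Care providers, study personnel and parents will be blinded to treatment assignment".

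The other places where a volume comparison between arms might appear do not supply one:

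- Section 4.0 makes the primary outcome the number of infants reaching full oral feeds and adds "We do not anticipate having power to compare any outcome with valid statistical measures". Daily volume is not listed as an endpoint.
- Section 10.0 uses each infant's own volume progress to decide whether crossover is offered: "If progress in daily oral feeding volumes is <4ml/kg/d (based on response rate in pilot trial) after 10 days".
- Section 12.0 says only "We do not anticipate being powered to determine efficacy in feeding response rate, or test for A/B or B/A effects".

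Section 5.0 admits infants who are "failing oral feeds after trying to learn feeding for 2 weeks if term, and 4 weeks if preterm".

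**The concern.** A before-after difference in these infants has at least three sources other than stimulation:

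- **Maturation and practice.** The protocol's background describes feeding as a skill that infants have to learn, with regular therapy as usual care. Volumes may rise with time alone.
- **Regression to the mean.** Infants enter because they are feeding poorly, and the 10 pre-treatment days can overlap the period that qualified them.
- **Extra attention during treatment.** Under section 10.0, feeders are trained by study staff and supervised during stimulated feeds. This happens in both arms, but not before treatment.

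All three are shared by active and sham infants, so they cancel in a comparison between arms. They do not cancel in a comparison of periods. Aim 2 is presented as a study of safety and efficacy that prepares for a later phase and a pivotal trial. A rise in volume that sham infants would also show could be carried forward as evidence of effect.

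**Working it through.** **No figure to reproduce.** The protocol gives no SD, drift, effect size or alpha for volume. From it come the two 10-day windows, 10 infants per arm, randomisation and the entry rule. Everything else below is an assumption, shown as a range.

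**1. Shift from steady drift.** Number the pre-treatment days -9 to 0 (mean -4.5) and the treatment days 1 to 10 (mean 5.5). The means are 5.5 - (-4.5) = 10 days apart. A drift of m ml/kg/d per day therefore shifts the before-after contrast by 10m. If volumes are flat before treatment and drift starts with it, the shift is 5.5m.

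| m (assumed) | Steady drift, 10m | Flat before, 5.5m | Expected active minus sham |
|---|---|---|---|
| 0 | 0 | 0 | 0 |
| 0.5 | 5 | 2.75 | 0 |
| 1 | 10 | 5.5 | 0 |
| 2 | 20 | 11 | 0 |

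**2. How often the contrast would mislead.** This was simulated with no device effect, 10 infants per arm and 20,000 runs per setting. The between-infant SD was 20 or 30 ml/kg/d and the correlation between windows was 0.5 or 0.7. The SD of change is SD × √(2(1 - r)), from 20 × √0.6 = 15.5 to 30 × √1 = 30. The table gives the share of runs in which the active arm's before-after 95% CI (paired t) excludes 0.

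| m | Steady drift | Flat before |
|---|---|---|
| 0 | 4.8% to 5.1% | as steady drift |
| 0.5 | 7.8% to 15.6% | 5.7% to 7.7% |
| 1 | 15.1% to 45.0% | 8.3% to 17.1% |
| 2 | 47.5% to 95.4% | 18.2% to 51.5% |

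The baseline-adjusted active-versus-sham CI excluded 0 in 4.6% to 5.3% of runs across all settings. A separate simulation, with the SD of change set at 15 to 25, agreed for n = 10 (21% to 47% at m = 1). With both arms pooled into one before-after test (n = 20), the rate at m = 1 rose to 40% to 81%.

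**3. Regression to the mean.** If entry selected the lowest fraction p on the 10-day pre-treatment mean, the expected rebound is (1 - r) × SD × φ(z_p)/p.

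- SD 20, r = 0.9, p = 0.5: 0.1 × 20 × 0.399/0.5 = 1.6 ml/kg/d.
- SD 30, r = 0.7, p = 0.25: 0.3 × 30 × 0.318/0.25 = 11.4 ml/kg/d.

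At r = 0.5, the lower correlation used in step 2, the second case would be 0.5 × 30 × 0.318/0.25 = 19.1 ml/kg/d. The actual entry rule is not a cut on the 10-day mean, so these figures indicate scale only.

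**4. Precision of the comparison between arms.** The 95% half-width is t(0.975, 17) × SD × √(2/10) × √(1 - r²), with t = 2.11.

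- SD 20: 16.3 (r = 0.5) and 13.5 (r = 0.7) ml/kg/d.
- SD 30: 24.5 (r = 0.5) and 20.2 (r = 0.7) ml/kg/d.

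Simulated mean half-widths ran from 13.6 to 25.0 ml/kg/d.

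**The case against.** The strongest reply is that the sentence comes straight after the active and sham arms are introduced, so before-and-during volumes within each arm may be what is meant. Nothing says that arms are pooled or that before-after change will be attributed to the device. The statement on A/B effects in section 12.0 suggests that treatment comparisons were considered. That reading is possible, and an analysis plan that was not seen may say so. But the protocol names a contrast, and the one it names is the weaker one. If a comparison by arm is intended, the edit only records the intention.

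Next, volume is neither the primary outcome nor a success criterion, and the protocol disclaims power. The first part stands and limits the importance of the point. The second does not answer it: power concerns precision, and a purely descriptive before-after figure carries the same shift.

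Third, the sizes are assumed. This stands. No test of volume is planned, so the exclusion rates are illustrations. Two to four weeks of failure plus a judgement that a G-tube is likely may mean a plateau, with m and the rebound near zero. The 4 ml/kg/d in section 10.0 does not settle m, because it can be read as a total over the 10 days or as a daily gain. On the first reading it corresponds to 0.4 per day, below every nonzero m used here. On the second it lies above them all.

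Last, the half-width of the proposed comparison (about 14 to 25) is as large as most of the biases considered. That is true, but such an interval shows its own uncertainty, whereas the before-after figure does not show its bias.

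**Conclusion.** The concern holds. As written, the only stated volume comparison cannot separate a device effect from change that would occur under sham, although the trial already has the randomised, blinded control needed to do so. The shift is 10m for steady drift (5.5m if volumes were flat before treatment), plus any regression to the mean. For assumed m of 0.5 to 2 this is 5 to 20 (2.75 to 11) ml/kg/d before any rebound, and it is zero if the infants have truly plateaued and entry selects no low point. The direction follows from the design, but the size rests wholly on assumed drift, SDs, correlations and selection. The point affects how a supporting efficacy measure is read. It does not affect the primary outcome, the safety outcomes or the sample size. It should be corrected, with medium confidence given that a comparison by arm may have been intended.

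**What to change.** Replace the volume sentence in section 1.0, Aim 2, with:

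> Mean daily oral volume (ml/kg/d) over the first 10-day treatment period, before any crossover, will be compared between active and sham as randomised, adjusted for the infant's mean over the 10 pre-treatment days, and reported descriptively as a difference with 95% CI. Before-after change will be shown by arm as description only.

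This changes analysis wording only. Both windows and both arms are already planned, so no infants, visits or measurements are added. The price is a wide interval at 10 per arm, which the report should state plainly.

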2.0 Background

Oromotor dyscoordination is common in preterm infants and in term infants who suffer HIE. Current standard of care consists of an occupational therapist working with infants once daily to encourage early feeding behaviors as early as 31 weeks gestational age (GA) or within a week of HIE birth. Therapists safely guide learning this motor skill and ensure that nipple flow rate and frequency of oral feeding do not tax infant physiology too greatly. Even with this therapy, feeding difficulty is the primary reason for delayed discharge ¹. In a recent Neonatal Research Network study, 37% of 6017 moderately preterm infants remain hospitalized beyond 36 weeks GA due to feeding difficulty ². These infants lose valuable developmental time in the hospital and have the highest risk for adverse neurodevelopmental outcomes.

If infants do not master this motor skill by late term age (42 weeks GA), they receive a G-tube for direct gastric feeding in order to be discharged to home. For example, in the Medical University of South Carolina (MUSC)'s NICU, an average of 40 G-tubes per year were placed from 2012-2016. MUSC's experience mirrors national data, which shows a doubling of G-tube insertion rates in infants from 2002 to 2012 ³. In another recent study, 5.5% of 12,621 preterm infants born between 23-33 weeks gestation had G-tubes placed for feeding difficulties⁴. This procedure exposes very young infants to anesthesia risks and has a high complication rate with recurrent emergency room visits and hospitalizations, adding to the cost burden for both the family and hospital. The G-tube also reinforces parental perception that their child is not normal and has a more limited developmental potential than a 'normal' child.

There is a clear unmet clinical need for new therapies that increase feeding motor development, accelerate time to discharge, and ultimately obviate G-tube insertion.

Any therapy that facilitates motor learning and enhances feeding skills would have a significant impact for infants who fail feeding rehabilitation. In addition, decreasing time to full oral feeds would offer significant costs savings for both hospitals and families. Decreasing gastrostomy tube placement (cost \$15,000) and length of stay (\$3000/day) due to feeding delays are major objectives of this technology.

With feeding delays in approximately 20% of 380,000 preterm infants and 4,000 term infants born with HIE in the US per year, as well as 76% of late preterm infants ¹⁰, this therapy may translate to a large number of infants and impact their outcomes. Moreover, if the portable taVNS system is successful in the targeted motor behavior of feeding, we plan to extend use of these devices and early neuromodulatory therapy in high-risk infants to prevent or mitigate other life-long motor problems, such as cerebral palsy. Thus, developing a commercial taVNS system for neonates and infants will provide a foundation for applying these devices in infants at high risk for motor problems who have few alternative treatments.

Etiology of feeding failure and relevance to our approach: Why do neonates with brain injury and some preterm infants fail to master oral feeding? Feeding involves sensorimotor integration of a complex sequence of sucking and swallowing, within a respiratory rate of 20-40 times a minute. Furthermore, feeding is the first sequential motor task that neonates must learn. The vagus and other nerves innervate muscles of the mouth, mandible, pharynx, and esophagus involved in feeding ¹¹⁻¹⁴. CNS injuries from brain dysmaturity in preterm infants¹⁵ or HIE injury in term infants, interrupt the developmental trajectory of vagal and other neural circuits^{15,}

Abnormal connections¹⁶, along with decreased populations of myelinating cells and inter-neurons, result in less myelination and fewer brainstem-cortical connections, and reduced corticobulbar regulation of both vagal activity and the muscles of the face, head, and neck^{14, 17}. In spite of developmental plasticity, the immature brain still has some of the worst outcomes following significant insult, and difficulty feeding is frequently the first manifestation of later motor and cognitive impairments¹⁶. Additionally, key sensorimotor cortical connections require activation during critical developmental windows, as for vision and hearing/language. A critical window is also postulated for oromotor skills ¹⁸. If illness delays feeding attempts, the feeding mechanism must be taught through rehabilitation, when it should be a normal reflex.

Neuroplasticity may be harnessed to improve outcomes and perhaps re-open developmental windows by activating neural connections or recruiting neurons as work-arounds for damaged circuits. Importantly, even with significant brain injury, we know that delivering neuromodulation during a task can harness activity- dependent plasticity and lead to improved, near-normal outcomes. In animal studies, pairing VNS with rehabilitative training increases cortical reorganization and functional outcomes after stroke or CNS injury, enhancing this activity-dependent plasticity ^{5, 19-22}. In April 2020, an FDA pivotal study of cervical-VNS paired with rehabilitation for adult stroke, reported clinically and statistically significant improvement with active paired VNS compared to sham (Microtransponder, [name] on DSMB). *Thus, the data in both animals and adult humans provide substantial evidence in support of the scientific premise of this proposal, that VNS paired with a stimulus improves functioning* ^{5, 19, 21-25}.

[name] has also shown via fMRI in adults that noninvasive taVNS activates key sensorimotor areas, including thalami and basal ganglia that are also areas of injury in HIE and preterm brain injury²⁶. Activating the afferent vagal fibers in the dorsal nucleus and locus coeruleus with an associated stimulus results in secretion of norepinephrine²⁷, a high-alert signal that helps re-establish normal connections if the vagus nerve is activated concurrently with a stimulus, whether **sensory** (tinnitus ²⁸⁻³⁰) or **motor** (upper limb after stroke ^{5, 31}).

Since suck-swallow is a complex sensorimotor sequence, both central vagus targets may be affected by taVNS during feeding to reinforce motor pattern learning. Furthermore, the non-invasive taVNS approach may be particularly effective in infants, whose developmental and reparative plasticity is greater than in adults.

